9.11. Clinical Global Impression of Severity

A brief Clinical Global Impression of Severity (CGIS) ([Busner, 2007](#)) questionnaire of the patient's condition will be completed at the visits outlined in [Table 1](#). The CGIS uses a 7-item scale to rate total severity whether or not, in the Investigator's judgment, it is due entirely to drug treatment. This rating is based upon observed and reported symptoms, behaviour, and function. The Investigator will compare the patient's current condition to that at Screening and determine how much the patient has changed on the following scale:

- 0 = not assessed
- 1 = normal, not at all ill
- 2 = borderline ill
- 3 = mildly ill
- 4 = moderately ill
- 5 = markedly ill
- 6 = severely ill
- 7 = among the most extremely ill patients

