 - Percentage of drinking days (PDD) in 85d prior D-3 (or start of detox) vs PDD post-dosing measured on d14, d28, d56, d84.
 - Mean Units per day (UPD): In 85d prior D-3 (or start of detox) vs UPD post-dosing measured on d14, d28, d56, d84.
 - Abstinence: Percentage of Abstinent days (PAD) in 85d prior D-3 (or start of detox) vs PAD on d14, d28, d56, d84 (with biomarker verification).
 - Number of days after BPL-003 dosing to first drink
 - Number of days after BPL-003 dosing to first HDD (defined by UK government as ≥ 7 units a day for a woman and ≥ 9 units per day for a man)
 - Average number of standard units of alcohol consumed per week in 85d prior D-3 (or start of detox) vs post-dosing measured on d14, d28, d56, d84 (and reported referencing UK risk levels)
- Consequences of alcohol use as measured by Short Inventory of Problems (SIP)
- Biomarkers
 - Alcohol use as measured by EtG in urine at Days 1, 28, 56, 84 compared to Screening
 - Alcohol use as measured by CDT in blood at Days 28 & 84 compared to Screening

Pharmacodynamic

- The correlation of the occurrence of a “complete mystical experience” and “ego dissolution”, measured by the MEQ-30 and EDI, with improvement in alcohol use and craving (measured by AQC, TLFB, EtG, CDT)

Wellbeing

- Change in Montgomery–Asberg Depression Rating Scale (MADRS) at Days 28, 56, and 84 compared to Baseline
- Change in Clinical Global Impression Severity (CGIS) at Days 1, 28, 56, and 84 compared to Baseline
- Patient Global Impression of Change (PGIC) at Days 1, 28, 56, and 84
- Change in 5-level EuroQol-5 Dimension (EQ-5D-5L) at Days 28 and 84 compared to Baseline

Expectation

- Assess positive and negative expectations as measured by Stanford Expectations of Treatment Scale (SETS)

Methods:

The following assessments will be made.

Safety and tolerability:

Patient safety will be assessed by laboratory assessments (routine haematology, clinical biochemistry, and coagulation), physical examinations, 12-lead ECGs, vital signs (blood pressure, heart rate, and temperature), and the C-SSRS. Adverse events (AEs) and concomitant medication will be recorded from Screening until the patient’s last visit. Nasal site reaction will be assessed after dosing.

Pharmacodynamic:

Mood, depression, and CGIS will be assessed at Screening, Days 0, 1, 28, 56, and 84.

BPL-003 subjective experiences will be assessed using the MEQ30 and the EDI.

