3.3. Exploratory Endpoints

Pharmacokinetic:

- Blood samples to determine 5-MeO-DMT and its metabolites (including bufotenine) plasma concentrations will be taken after dosing on Day 0.

Drinking Craving:

- Change in alcohol craving as measured by Alcohol Craving Questionnaire (ACQ) at Days 1, 7, 28, 56, and 84 compared to Baseline (pre-dose on Day 0)
- Alcohol cravings as measured by Craving Visual Analogue Scale (VAS)
- Alcohol withdrawal symptoms as measured by Clinical Institute Withdrawal Assessment (CIWA-Ar)
- Consequences of alcohol use as measured by Short Inventory of Problems (SIP)

Alcohol Use:

Using the Timeline Follow-Back (TLFB) interview, the following parameters of alcohol use in the 90 days before dosing and endpoint will be recorded:

- Percentage of Heavy Drinking Days (PHDD) in 85d prior D-3 (or start of detox) vs PHDD post-dosing measured on d14, d28, d56, d84.
- Percentage of drinking days (PDD) in 85d prior D-3 (or start of detox) vs PDD post-dosing measured on d14, d28, d56, d84.
- Mean Units per day (UPD): In 85d prior D-3 (or start of detox) vs UPD post-dosing measured on d14, d28, d56, d84.
- Abstinence: Percentage of Abstinent days (PAD) in 85d prior D-3 (or start of detox) vs PAD on d14, d28, d56, d84 (with biomarker verification).
- Longest duration (days) of continuous abstinence
- Number of days after BPL-003 dosing to first drink
- Number of days after BPL-003 dosing to first HDD (defined by UK government as >7 units a day for a woman and >9 units per day for a man)
- Average number of standard units of alcohol consumed per week in 85d prior D-3 (or start of detox) vs post-dosing measured on d14, d28, d56, d84 (and reported referencing UK risk levels)
- Maximum number of standard units of alcohol consumed on any one day

Correlation of PD effects with alcohol use and related symptoms

The correlation of the occurrence of a “complete mystical experience” and “ego dissolution”, measured by the MEQ30 and EDI, with improvement in alcohol use and craving (measured by AQC, TLFB, EtG, CDT)

Biomarkers

- Alcohol use as measured by EtG in urine at Days 1, 28, 56, 84 compared to Screening
- Alcohol use as measured by CDT in blood at Days 28 & 84 compared to Screening

Wellbeing

- Change in Montgomery–Asberg Depression Rating Scale (MADRS) at Days 28, 56, and 84 compared to Baseline
- Change in Clinical Global Impression Severity (CGIS) at Days 1, 28, 56, and 84 compared to Baseline

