4. INVESTIGATIONAL PLAN

4.1. Overall Study Design

Study BPL-003-203 is an open-label, dual-centre, Phase 2a study to evaluate the safety, tolerability, and PD effects of a single intranasal dose of BPL-003 combined with relapse prevention psychotherapy to assess the treatment model and explore the potential effects on alcohol use and related symptoms. This study will assess a dry powder benzoate formulation of 5-MeO-DMT (BPL-003). Enrolment of up to 12 patients with AUD is planned in up to 2 cohorts (Cohorts 1 and 2). Patients will receive a single dose of 10mg (Cohort 1) or 12mg (Cohort 2) BPL-003.

After completing the screening period, those patients who are confirmed as eligible will participate in a minimum of 3 preparatory sessions over approximately 2 weeks before the BPL-003 treatment session. These psychological support sessions will be conducted by a therapist with psychedelic knowledge and the alcohol use disorder therapist. The last of the 3 sessions will be conducted at the clinic where the dosing will occur so that patients can become familiar with the dosing room, clinic staff and a practice run with the nasal delivery system can be completed. Baseline assessments will be completed on the BPL-003 treatment day, before BPL 003 administration. BPL-003 will be administered on the treatment day in accordance with established safety practices for psychedelic research. A minimum of 3 integration sessions will occur over approximately 2 weeks after the treatment session, together with AUD relapse prevention psychotherapy ([Appendix 4](#) for details) that will guide the patient through the 12-week, post-dose follow-up period.

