9.12. Patient Global Impression of Change

A brief PGIC will be completed at the visits outlined in [Table 1](#). The PGIC uses a 7-item scale to rate total improvement reported by patient whether or not it is due to drug treatment. The patient will report their own current condition compared to that at Screening on the following scale:

- 0 = Not assessed
- 1 = Very much improved
- 2 = Much improved
- 3 = Minimally improved
- 4 = No change
- 5 = Minimally worse
- 6 = Much worse
- 7 = Very much worse

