- **Dosing visit:** After completion of the 3 preparatory sessions, patients will attend the clinic for their dosing visit. Patients will be resident at the clinic from the morning of Day 0 (dosing day) until at least 4 hours postdose. BPL-003 will be administered to patients in the designated setting, and the therapist will remain with patients while patients are in an altered state of consciousness.
- **Qualitative interview (optional):** After return to a usual state of consciousness after dosing, and provided they consent, patients will be asked to have a one-to-one guided

qualitative interview with independent researchers trained in microphenomenology methods to discuss their psychedelic experience (as detailed in the Qualitative Interview Study Manual). This will be done either face to face at the clinic or via video call. Psychometric scales will then be administered to provide quantitative measures of the patient's psychedelic experience.

All patients will have their readiness for discharge assessed every 30 minutes starting 90 minutes after dosing before discharge on the dosing day. The earliest a patient can be discharged will be 4 h after receiving the dose.

- **Follow-up (for 12 weeks postdose):**
 - **Psychedelic integration sessions:** Patients will have at least 3 integration sessions, lasting approximately 60-90 min, over the 2 weeks following their dose to discuss their experience with the therapists.
 - **Relapse prevention psychotherapy:** Patients will have weekly sessions following the dose of BPL-003 as defined in the AUD Therapy Manual (can be either face to face or remote) with an AUD therapist.

6 Schedule of events

Please refer to Table 1 of the protocol, version 7, dated 29 August 2024

7 Planned analyses

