			85 Days Prior Day-3	Day 14	Day 28	Day 56	Day 84	85 Days Prior Day-3	Day 14	Day 28	Day 56	Day 84			85 Days Prior Day-3	Day 14	Day 28	Day 56	Day 84
		x	x	x	x	x	x	x	x	x	x	x			x	x	x	x	x

listing continued

Treatment	Patient	Percentage of Heavy Drinking Days (PHDD)					Percentage of Drinking Days (PDD)					Mean Units per Day (UPD)					Abstinence: Percentage of Abstinent Days (PAD)				
		85 Days Prior Day-3	Day 14	Day 28	Day 56	Day 84	85 Days Prior Day-3	Day 14	Day 28	Day 56	Day 84	85 Days Prior Day-3	Day 14	Day 28	Day 56	Day 84	85 Days Prior Day-3	Day 14	Day 28	Day 56	Day 84
		x	x	x	x	x	x	x	x	x	x	x	x	x	x	x	x	x	x	x	x

Note: 85 Days Prior Day -3 = 85 Days Prior Day -3 (or start of detox)

Template L_PD7_PG

Listing 16.2.x.xx Listing of Alcohol Craving Questionnaire (ACQ)

Treatment	Patient	Planned Relative Time	Date/Time	Question 1	Question 2	Etc.
		Time 1	26SEP2012:09:57	x		

Template L_PD8_PG

Listing 16.2.x.xx Listing of Clinical Global Impression-Severity (CGI-S)

Treatment	Patient	Planned Relative Time	Date/Time	Considering your total clinical experience with this patient population, how ill is the patient at this time?
		Time 1	26SEP2012/09:57	0

Programming notes: For PGIC use "Since the start of the study, my overall status is"

Template L_PD9_PG

Listing 16.2.x.xx Listing of Clinical Institute Withdrawal Assessment for Alcohol- Revised (CIWA-Ar)

Treatment	Patient	Planned Relative Time	Date/Time	Nausea and vomiting	Tremor	Paroxysmal Sweats	Etc.
		Time 1	26SEP2012:09:57	x	x	x	x

Template L_AE1_PG

Listing 16.2.x.xx Listing of all adverse events

Treatment	Patient	System Organ Class* / Preferred Term/ Verbatim Text	Outcome/ Onset Date/Time/ Resolved Date/Time/ Duration	Study Day Started/ Time Since Last Dose	Severity/ Serious/ Withdrawal/AESS/ AESI	Frequency/ Action Taken (1)/ Other Action Taken	Related to Study Drug/ Treatment Emergent?
Treatment 1	1001	Gastrointestinal Disorders / Intestinal Spasm / Entero-spasm	Resolved/ 24SEP2003 13:05/ 27OCT2003 7:50/ 34d 4h 5m	Day x/ 10d 7h 3m	Mild/ No/ Yes	Intermittent/ Dose not changed/ None	Possibly/ Yes

(1) Action Taken with Study Treatment

*Coded using MedDRA vXX.X

AESS = Adverse event of special situation

AESI = Adverse event of special interest

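### CGIS has no pre-dose Day 0 rating in Table 1, so its change from baseline starts at Screening and includes the run-in; the rater instruction in protocol 9.11 also does not fit the severity scale

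*Protocol*

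**What the plan says.** The endpoint in protocol 3.3 is "Change in Clinical Global Impression Severity (CGIS) at Days 1, 28, 56, and 84 compared to Baseline". Protocol 4.1 says that "Baseline assessments will be completed on the BPL-003 treatment day", before the drug is given.

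The CGIS row of Table 1 marks Screening and Days 1, 28, 56 and 84; the Day 0 cell is empty. Table 1 is the governing schedule: protocol 9.11 says the "questionnaire of the patient's condition will be completed at the visits outlined in" that table, and SAP section 6 says "Please refer to Table 1 of the protocol, version 7, dated 29 August 2024". The synopsis (Methods, Pharmacodynamic) has a joint sentence: "Mood, depression, and CGIS will be assessed at Screening, Days 0, 1, 28, 56, and 84".

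Protocol 11.6 and SAP 12.2 define baseline as the last pre-dose value, with Screening used when there is no pre-dose Day 0 or Day -3 value.

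Protocol 9.11 says the scale rates total severity and lists anchors from 1 (normal) to 7 (among the most extremely ill). It also tells the Investigator to compare the patient's "current condition to that at Screening and determine how much the patient has changed on the following scale". SAP listing template L_PD8_PG words the item as "how ill is the patient at this time". SAP template T_PD6 treats the score as continuous and gives change-from-baseline columns, waived only for PGIC.

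**The concern.** In a single-arm study the within-patient change is the only comparison available, so the choice of baseline decides what the number means. The interval from Screening to dosing is not inactive. Patients have three preparation sessions, relapse-prevention therapy starts during those sessions (Table 1, note 15; Appendix 4, Stage 1), and they must have no heavy drinking day in the 72 hours and no alcohol in the 24 hours before dosing. If a patient's global severity shifts over those weeks, the shift is tabulated as CGIS change after BPL-003. Day 1 is the most exposed visit.

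The second problem is in the instruction. A rater told to judge change, but given only severity levels to choose from, may let the comparison with Screening colour the score. The SAP then subtracts the Screening score as well. With up to 12 patients at two sites, uneven reading of the instruction could show.

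**Working it through.** The documents give no figure for this point, so there is none to reproduce. The check sets the schedule against the baseline rule and then uses calendar arithmetic.

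**Step 1: visits in Table 1.** Each of these rows reads as 18 cells against the 18 visit columns, so the empty CGIS cell is not a shifted column.

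| Scale | Pre-dose | Post-dose |
|---|---|---|
| CGIS | Screening | Days 1, 28, 56, 84 |
| MADRS | Screening, Day 0 | Days 28, 56, 84 |
| ACQ | Day 0 | Days 1, 7, 28, 56, 84 |
| PGIC | none | Days 1, 28, 56, 84 |

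**Step 2: baseline rule.** CGIS has neither a Day 0 nor a Day -3 rating, so its baseline is Screening, which Table 1 places at Day -28 to -14.

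**Step 3: share of each change interval that precedes the dose.** Let s be the days from Screening to dose (14 or 28) and d the post-dose day. Share = s / (s + d), in nominal days.

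| Visit | s = 14 | s = 28 |
|---|---|---|
| Day 1 | 14/15 = 93.3% | 28/29 = 96.6% |
| Day 28 | 14/42 = 33.3% | 28/56 = 50.0% |
| Day 56 | 14/70 = 20.0% | 28/84 = 33.3% |
| Day 84 | 14/98 = 14.3% | 28/112 = 25.0% |

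With a pre-dose Day 0 baseline, s = 0 and every share is 0%.

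**Step 4: what this can do to a score (assumed values).** Take a Screening score of 5 and a Day 28 score of 3. Change from Screening is 3 - 5 = -2 whatever happened in between. Change from Day 0 is 3 - 5 = -2, 3 - 4 = -1 or 3 - 3 = 0, according to whether the pre-dose score was 5, 4 or 3. The Screening-based figure cannot tell these patients apart.

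**Step 5: does the synopsis promise a Day 0 CGIS?** The union of the MADRS visits (Screening, 0, 28, 56, 84) and the CGIS visits (Screening, 1, 28, 56, 84) is Screening, 0, 1, 28, 56, 84, which is exactly the synopsis list. Read scale by scale, the sentence would also put MADRS on Day 1, which neither Table 1 nor the MADRS endpoint has. The sentence is therefore ambiguous.

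**Step 6: instruction against scale.** The change instruction in 9.11 has no matching response option, since all seven rated anchors are severity levels. It has no meaning at the Screening visit itself. It also differs from the SAP item, "how ill is the patient at this time". A baseline subtraction makes sense only if raters score current severity.

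**The case against.** The strongest case for the plan is that a Screening baseline is already provided for. Both documents state the fallback, and CGIS is not alone: EQ-5D-5L is also collected only at Screening before the dose, and EtG and CDT are expressly compared with Screening. The exploratory objective concerns the dose combined with relapse-prevention psychotherapy, which begins during preparation, so a Screening reference can be defended as describing the whole package. Nothing in the endpoint claims to isolate the drug. That argument stands as far as it goes, but it supports labelling the result as change from Screening. It does not sit easily with the statement that baseline is taken on the treatment day, and it is weakest at Day 1, where the interval is nearly all run-in.

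A reader might infer more than the documents support:

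- That the synopsis requires a Day 0 CGIS and Table 1 dropped it. Step 5 shows the sentence need not mean that.
- That both MADRS and ACQ isolate the first post-dose change. Only ACQ has both a Day 0 and a Day 1 rating; the first post-dose MADRS is on Day 28.
- That scores are being differenced twice. This happens only if raters follow the 9.11 sentence literally. The same paragraph calls the scale a severity rating, and the SAP item asks for current severity.
- That PGIC is also wrong. Protocol 9.12 openly asks for the patient's "current condition compared to that at Screening on the following scale", and the SAP prompt refers to the start of the study. Anchoring it to dosing instead would ask a different question, and the choice is one of preference.

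**Conclusion.** The point holds as a minor one. As scheduled, CGIS change from baseline is change from Screening and includes any change during the run-in. By time, that is 93-97% of the interval at Day 1, falling to 14-25% at Day 84. A reader might take these percentages as the part of the CGIS effect that is not due to the dose, or assume that patients improve before dosing. Neither is supported: the percentages are shares of nominal calendar time, and the documents show neither the amount nor the direction of pre-dose change. Patients may also enter up to 14 days after their last heavy drinking day or after completing detoxification, so severe illness at Screening cannot be presumed.

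The conclusion assumes that sites follow Table 1. If a site rates CGIS before dosing on Day 0, the baseline rule will take that value. A Day 0 baseline removes the run-in component but does not separate the drug from psychotherapy that continues after dosing.

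The 9.11 sentence conflicts with its own anchors, the SAP item and the SAP subtraction whatever baseline is used. No primary or secondary endpoint is affected, and the study tests no hypothesis.

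**What to change.** 1. In protocol 9.11, replace the instruction to judge change since Screening with the current-severity question already worded in SAP listing template L_PD8_PG. This costs one sentence.
2. Add a pre-dose Day 0 CGIS to Table 1, reconcile the synopsis sentence with it, and name that rating in the SAP as the baseline for Table 14.2.10. This costs one single-item Investigator rating at a visit where MADRS is already done. For patients already dosed without it, label the result 'change from Screening'.
3. Leave PGIC anchored to Screening. A footnote to Table 14.2.11 saying that it includes the preparation period is optional.

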9.12. Patient Global Impression of Change

A brief PGIC will be completed at the visits outlined in [Table 1](#). The PGIC uses a 7-item scale to rate total improvement reported by patient whether or not it is due to drug treatment. The patient will report their own current condition compared to that at Screening on the following scale:

- 0 = Not assessed
- 1 = Very much improved
- 2 = Much improved
- 3 = Minimally improved
- 4 = No change
- 5 = Minimally worse
- 6 = Much worse
- 7 = Very much worse

9.13. Clinical Institute Withdrawal Assessment for Alcohol-Revised

The Clinical Institute Withdrawal Assessment for Alcohol-Revised (CIWA-Ar) ([Saitz, 1994](#); [Sullivan, 1989](#)) is a 10-item scale used in the assessment and management of alcohol withdrawal. Each item on the scale is scored independently, and the summation of the scores yields an aggregate value that correlates to the severity of alcohol withdrawal. The ranges of scores are designed to prompt specific management decisions such as the administration of benzodiazepines. The maximum score is 67; mild alcohol withdrawal is defined by a score ≤ 10 , moderate by scores 11 to 15, and severe by any score ≥ 16 .

9.14. Short Inventory of Problems

The Drinker Inventory of Consequences (DrInC) was developed to assess consequences of alcohol use; it contains 50 items, 45 of which measure consequences in 5 domains: interpersonal, intrapersonal, physical, impulse control, and social. In the briefer 15-item version of this measure, the Short Inventory of Problems (SIP), 3 items from each of the 5 domains based on the strongest item–subscale correlations were selected. Revised versions use the 15 items with the strongest item–total correlations ([Blanchard, 2003](#)). The version used in this study is the SIP-2R developed by the Center on Alcohol, Substance use, And Addictions (CASAA) at the University of New Mexico. A sample of the SIP-2R questionnaire is provided in [Appendix 2](#).

9.15. Readiness for discharge questionnaire

An appropriately trained member of the site team will complete the readiness to discharge questionnaire to determine the earliest timepoint the patient is able to leave the clinical study site safely. The postdose vital signs (HR, BP and temperature), done every 30 min, are included as part of this questionnaire. Patients will have their readiness for discharge assessed every 30 min starting 90 min after dosing, up to the point the patient has been deemed safe to leave the clinical study site. The final readiness to discharge questionnaire will be verified by a suitable physician. If the final readiness to discharge is before the 4 h postdose timepoint the patient will remain until 4 h postdose as per this protocol. Completion of the readiness to discharge questionnaire can stop once the patient has been deemed safe to leave the clinical study site as per the questionnaire. If the patient is not ready for discharge at 4 hours postdose then the questionnaire will be repeated again at the point Investigator believes patient may be ready for discharge.

9.16. Treatment model Feedback

Feedback on the treatment model will be sought from therapists on the frequency and duration of psychotherapy sessions, implementation of therapy manual and overall therapy model. Feedback will be obtained in a qualitative interview to be conducted by the Beckley Medical Monitor or delegate individually with each therapist following completion of each patient's integration sessions. It will be completed once per patient, and occur between Day 15 to Day 42.

9.17. Biomarkers

9.17.1. Ethyl Glucuronide

Ethanol is excreted from the body in a variety of ways, including

- Direct excretion of ethanol (5%-10%) in urine, sweat, and breath
- Metabolic excretion by conversion to acetaldehyde or acetic acid (>90%)
- Metabolic excretion by conversion to ethyl glucuronide (EtG) and ethyl sulfate (<0.1%), both of which are readily eliminated through urination

While most of these excretory products are detectable in urine for very short periods of time (<24 hours), EtG has a longer half-life and may be detectable in urine for up to 72 hours after consumption, depending on the dose taken prior to specimen collection. Although higher amounts of EtG might indicate greater alcohol consumption, the exact EtG number is influenced by several factors, including how recently alcohol was consumed. The presence of EtG in urine indicates only that the individual was exposed to ethanol at some point in the recent past before testing, typically within the preceding 72 hours.

There are some limitations to this test. It can produce a positive test from the mere exposure to alcohol that is present in many daily-use products, e.g., mouthwashes, breath sprays, foods prepared with or flavored with alcohol, and hand sanitizers. Therefore, a positive test should be confirmed either with another test or with verification from the patient that he or she did indeed drink alcohol. However, the EtG test accurately detects a person who recently consumed alcohol 70% or more of the time. One study showed that for moderate to heavy drinking, this value increases to 85% ([Shukla, 2017](#)).

